9.3.1. Primary Safety Analysis: Safety Lead-In (Cohorts I and II) and Cohort III-V

The primary objectives for the Safety Lead-in are to assess safety and tolerability of MT-401 manufactured using peptides produced by two different vendors, including identifying DLTs. The primary objective for Cohort III is to assess the safety and tolerability of a higher dose than the dose used in the Phase 2 portion of the study. The primary objective for Cohorts IV-V is to assess the safety and tolerability of the accelerated MT-401 product. For both the Safety Lead-in, which includes Cohorts I and II, and Cohorts III-V, the number of DLTs per cohort will be identified as defined in Section 5.6. The confirmed dose and peptide manufacturer will be identified based on the procedures of the standard 3+3 design described in Section 4.5 and review of entirety of the safety data. Safety endpoints will be analyzed as discussed in Section 9.3.5.

9.3.2. Primary Efficacy Analysis: Group 1

The primary endpoint for Group 1 is RFS, defined as the time between the date of randomization and the date of first relapse per ELN recommendations or death by any cause, whichever occurs first. For patients who remain alive and whose disease has not relapsed, RFS will be censored on the date of last evaluable disease assessment. For patients who remain alive and have no recorded post-randomization disease assessment, RFS will be censored on the date of randomization. Censoring rules for the primary analysis of RFS in Group 1 are presented in Table 9.

Relapse includes either hematologic and/or molecular relapse as defined in Table 6 at any disease assessment.

Confidential Page 52 of 74

For the interim analysis, RFS as determined by the investigator will be used.

Table 9: Censoring Scheme for Primary definition of RFS

Situation	Date of Event or Censoring	Outcome
Relapse per ELN recommendations	Date of first relapse	Event
Death without relapse	Date of death	Event
No baseline disease assessment	Date of randomization	Censored
No on-study disease a ssessments and no death	Date of randomization	Censored
No relapse and no death	Date of last evaluable disease	Censored
	assessment	
New anti-cancer therapy received without relapse	Date of last evaluable disease	Censored
reported prior to or on the same day as disease	assessment on or prior to the date of	
assessment	initiation of subsequent therapy	
Two or more consecutive missed scheduled disease	Date of last evaluable disease	Censored
assessments	assessment prior to the missed disease	
	assessments	

Abbreviations: AML=acute myeloid leukemia; RFS=relapse-free survival

RFS curves will be estimated using the Kaplan-Meier (KM) product limit method. For Group 1, the hazard ratio and corresponding 95% confidence interval (CI) will be estimated using a Cox proportional hazards model using randomized arm and two stratification factors as covariates. The KM estimate of the medians will be reported, and the corresponding 95% CI will be computed. KM estimates of RFS rates at milestone time points will be reported along with two-sided 95% CIs using Greenwood's formula, provided the minimum follow-up in patients exceeds the time point to support stable estimation of the rate. In addition to the Cox model, a stratified log-rank test will be used to compare the treatment arms, stratified by pre-transplant MRD status (MRD+ vs. MRD-/Unknown) and cytogenetic risk (Unfavorable vs. Other).

RFS is defined as the time between the date of first dose and the date of first relapse per ELN recommendations or death by any cause for Group 2 patients, and will be summarized for Group 2 Subgroup D patients and those in Group 2 who are in CR_{MRD} prior to administration of MT-401.

9.3.3. Primary Efficacy Analysis: Group 2

The primary endpoints for Group 2 are CR rate and duration of complete response. For Group 2 Subgroup C, CR rate is defined as the proportion of treated patients who achieve a best response of CR_{MRD} - or CR using the ELN recommendations. For Group 2 Subgroup D, CR rate is defined as the proportion of treated patients who achieve a best response of CR_{MRD} -. Best overall response (BOR) is defined as the best response designation recorded between the date of first dose and the date of objectively documented progression or relapse per ELN recommendations or the date of subsequent therapy, whichever occurs first. For patients without documented progression or subsequent therapy, all available response designations will contribute to the BOR assessment.

The primary analysis will occur after all patients treated have been followed for 6 months.

For Group 2 Subgroup C, duration of complete response is defined as the time between the date of first documented response of CR_{MRD}- or CR to the date of the first documented relapse per ELN recommendations or death due to any cause, whichever occurs first. For Group 2 Subgroup D, duration of

Confidential Page 53 of 74

complete response is defined as the time between the date of first documented response of CR_{MRD} - to the date of the first documented relapse per ELN recommendations or death due to any cause, whichever occurs first.

The CR rate from Group 2 Subgroup C will be evaluated in the context of results from an ongoing retrospective study of AML patients who are similar to the inclusion/exclusion criteria of Group 2 Subgroup C patients. Any comparison of Group 2 data to results from the retrospective study will be described in a separate SAP.

Censoring rules for DOCR are provided in Table 10.

Table 10: Censoring Scheme for Primary Definition of DOCR

Situation	Date of Event or Censoring	Outcome
Relapse per ELN recommendations	Date of first relapse	Event
Death without relapse	Date of death	Event
No relapse and no death	Date of last evaluable disease assessment	Censored
New anti-cancer therapy received without relapse reported prior to or on the same day as disease assessment	Date of last evaluable disease assessment on or prior to the date of initiation of subsequent therapy	Censored
Two or more consecutive missed scheduled disease assessments	Date of last evaluable disease assessment prior to the missed disease assessments	Censored

Abbreviations: AML=acute myeloid leukemia; RFS=relapse-free survival

Relapse includes either hematologic and/or molecular relapse as defined in Table 6 at any disease assessment.

The CR rate and the corresponding 95% exact CI will be calculated. The DOCR will be estimated using the KM product limit method. The KM estimate of the median DOCR and the DOCR rates at milestone timepoints will be reported along with the two-sided 95% CI.

9.3.4. Secondary Analyses

9.3.4.1. Overall Survival (Groups 1 and 2)

Overall survival is defined as the time from randomization (Group 1) or first dose (Group 2) to the date of death. A patient who has not died will be censored on their last contact date ("last known alive date").

The statistical methods for analyzing OS are identical to those described for RFS.

Patients in Group 2 who achieve CR_{MRD}. post-bridging therapy will be summarized separately for OS.

9.3.4.2. Graft-versus-host Disease- and Relapse-free Survival (Groups 1 and 2)

Graft-versus-host disease- and relapse-free survival (GRFS) is defined as the time from randomization (Group 1) or first dose (Group 2) to date of GVHD, relapse, or death, whichever occurs first. GVHD events are defined as any grade 3-4 acute GVHD or chronic GVHD requiring systemic therapy. A patient who has not experienced any of these events will be censored on the date of their last evaluable disease

Confidential Page 54 of 74

assessment. For patients who remain alive and have no recorded post-baseline disease assessment, GRFS will be censored on the date of randomization (Group 1) or first dose (Group 2). Censoring rules for the analysis of GRFS in Group 1 are presented in Table 11.

Table 11. Censoring Scheme for Primary Definition of GRFS

Situation	Date of Event or Censoring	Outcome
GVHD or relapse	Date of first event type	Event
Death without GVHD or relapse	Date of death	Event
No baseline disease assessment	Date of randomization	Censored
No on-study disease assessments and no death	Date of randomization	Censored
No GVHD, no relapse, and no death	Date of last evaluable disease	Censored
	assessment	
New anti-cancer therapy received without relapse	Date of last evaluable disease	Censored
reported prior to or on the same day as disease	assessment on or prior to the date of	
assessment	initiation of subsequent therapy	
Two or more consecutive missed scheduled disease	Date of last evaluable disease	Censored
assessments	assessment prior to the missed disease	
	assessments	

Abbreviations: AML=acute myeloid leukemia; GRFS=graft-versus-host disease relapse-free survival

The statistical methods for analyzing GRFS are identical to those described for RFS.

GRFS will be summarized for Group 1 and Group 2 Subgroup D, respectively.

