c Intervention Period includes study treatment and Active Follow-up and Survival Follow-up as defined in Section 4.4 (including for Safety Lead-in portion of the study). Day 0/Week 0 is considered the day of the first infusion of MT-401 (which differs from the Day 1 used for allogeneic HSCT). Each infusion and visit must be at least 2 weeks apart. Active Follow-up Period as defined in Section 4.4: occurs after the last dose of MT-401 has been administered until patient relapses/progresses or declines additional study visits. Timing of Follow-up Visits are in relation to the timing of the Day 0 visit. Sponsor will schedule Day 0 timing for all patients in all groups, including Group 1 SoC arm.

d SoC patients do not need to perform visit Weeks 2 or 4, unless clinically indicated. Week 0 visit for SoC patients may occur between days 85-130 post-HSCT, as instructed by Sponsor.

^e Survival follow-up begins after relapse/progression or active follow-up is completed and occurs every 3 months for 3 years, every 6 months for the remainder of the study (which can be phone contact to collect patient survival status [if alive, last date known alive, and if dead, date of death], and collect any additional anticancer therapy post-MT-401 or SoC received during study.

Confidential Page 19 of 74

f Brief physical exam, to include at a minimum, assessments of the Cardiovascular, Respiratory, and Gastrointestinal systems (height and weight will be needed at screening at minimum and any changes recorded if >10%).

g Pregnancy testing is required unless a patient has no possibility of being pregnant (for example post-hysterectomy). Perform as clinically indicated during intervention period for WOCBP. See Section 8.3.5 for details.

^h On day of MT-401 administration, laboratory assessments and/or disease assessments are completed prior to infusion (see Section 8.2.3 for additional details of laboratory assessments to be performed).

¹ Vital signs obtained within 1 hour pre- and post-infusion (window ± 15 min).

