^j Disease assessment will be performed on blood, bone marrow samples, and/or other tissue samples at these time-points. For Group 1 and Group 2, the screening disease assessment may be performed as part of SoC (prior to consent if it was already completed). For Group 1, pre-transplant testing of MRD should be performed locally by any testing methodology and results recorded in the eCRF. Post-transplant baseline MRD testing will be performed centrally, and results must be available prior to randomization. If any additional disease assessments, such as additional time points or additional testing (e.g., imaging for extramedullary disease), or visits occur due to clinical necessity, information will be recorded on eCRF. Includes central testing for MRD status for all samples collected as per SoC and as per standard institutional guidelines at other time points by methods outlined in protocol in Section 4.1 (samples stored for central confirmation at later date). If imaging is performed on a patient, the Sponsor may request imaging to be sent to a central vendor along with any disease assessment reports.

Disease assessment at Day 0 for Group 1 only (disease assessment does not need to be repeated if within 3 weeks of prior disease assessment and results can be pending prior to treatment).

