- Graft-versus-host disease RFS (GRFS): defined as the time from randomization to date of GVHD, relapse, or death, whichever occurs first. A GVHD event is defined as any grade

3-4 acute GVHD or chronic GVHD requiring systemic therapy. A patient who has not experienced any of these events prior to analysis cutoff or the start of new anti-cancer therapy, will be censored on the earlier date of their last GVHD assessment and evaluable disease assessment demonstrating no relapse prior to analysis cutoff or start of new therapy. For patients who remain alive and have no baseline disease assessment or have no recorded post-randomization disease assessment, GRFS will be censored on the date of randomization. In addition, if a GVHD event, relapse, or death occurs after extended time without GVHD assessments, GRFS will be censored on the date of the last evaluable GVHD assessment prior to the missed GVHD assessments or on the date of the last GVHD assessment prior to the missed GVHD assessments.

Phase 2 Active Disease (Group 2):

- ORR: defined as the proportion of treated patients who achieve a best response of CR_{MRD}-, CR, CRi, MLFS, or PR using the ELN recommendations and repeated MRD assessment. This endpoint only applies to Group 2 Subgroup C.
- DOR: defined as the time between the date of first documented response of CR_{MRD}-, CR, CRi, MLFS, or PR to the date of the first documented progression per ELN recommendations or death due to any cause, whichever occurs first. For patients who neither progress nor die prior to analysis cutoff or the start of new anti-cancer therapy, DOR will be censored on the date of their last evaluable disease assessment on or after the assessment of first documented CR_{MRD}-, CR, CRi, or PR and prior to analysis cutoff or start of new therapy. This endpoint only applies to Group 2 Subgroup C.
- PFS: defined as the time between the date of first dose and the date of documented progression or death by any cause, whichever occurs first. For patients who remain alive and whose disease has not progressed prior to analysis cutoff or the start of new anti-cancer therapy, PFS will be censored on the date of last evaluable disease assessment prior to analysis cutoff or start of new therapy. For patients who remain alive and have no baseline disease assessment or have no recorded post-dose disease assessment, PFS will be censored on the date of first dose of study medication. This endpoint only applies to Group 2 Subgroup C.

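### GRFS rules conflict: GVHD is an event on its date, yet a living patient with no post-baseline disease assessment is censored at time zero even if qualifying GVHD is recorded

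*Protocol*

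**What the plan says.** Protocol 9.3.4.2 defines the GVHD component: "GVHD events are defined as any grade 3-4 acute GVHD or chronic GVHD requiring systemic therapy". The first row of Table 11 makes GVHD or relapse an event, dated "Date of first event type". Two rows with the opposite outcome matter here:

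- "No on-study disease assessments and no death": censored at randomization. The row excludes deaths but not GVHD.
- "No GVHD, no relapse, and no death": censored at the last evaluable disease assessment. This row does exclude GVHD.

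The text above the table applies the first of these to every living patient without a post-baseline disease assessment, from randomization in Group 1 and from first dose in Group 2. SAP 6.4.1.3 agrees: patients who are alive and "have no recorded post-randomization disease assessment, GRFS will be censored on the date of randomization". SAP 7.4.7.2 lists GRFS among the endpoints for which a patient with no baseline or no post-baseline disease assessment is censored at 1 day. It makes no exception for GVHD or for death.

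In the Schedule of Activities (Protocol Table 1), GVHD is assessed at Baseline, Weeks 0, 2, 4 and 12, and later. After Day 0 the next disease assessment is at Week 12. The Day 0 disease assessment is for Group 1 only, and the "disease assessment does not need to be repeated if within 3 weeks of prior disease assessment". Footnote d adds: "SoC patients do not need to perform visit Weeks 2 or 4, unless clinically indicated".

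**The concern.** The censoring row has the same form as the RFS row in Table 9. There it is safe: relapse is found by disease assessment, so a living patient with none has no observed event. GVHD is assessed separately, so in GRFS the same patient can have a recorded event. One programmer, following the first row of Table 11, would count it. Another, following SAP 6.4.1.3 or 7.4.7.2 literally, would delete it and give the patient no follow-up.

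GRFS is the efficacy endpoint meant to show whether relapse control comes at the price of GVHD. A rule that can drop recorded GVHD works against that purpose, and in an open-label trial the choice should not be left to programming.

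**Working it through.** The documents give no GRFS event count, power or GVHD rate, so there is no plan figure to reproduce. The check is a comparison of the rules followed by timing arithmetic.

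**1. Do the rules overlap?** Take a living patient with grade 3-4 acute GVHD and no disease assessment after baseline by the cutoff.

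| Rule | Result |
|---|---|
| Table 11, GVHD or relapse row | Event on the GVHD date |
| Table 11, no on-study assessment row, and matching text | Censored at randomization |
| SAP 6.4.1.3 | Censored at randomization |
| SAP 7.4.7.2 | Censored at 1 day |

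No order of precedence is given. The overlap is real.

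**2. Who can be in it?** The patient must have no post-baseline disease assessment up to the cutoff. GVHD at Week 2 followed by a Week 12 assessment stays an event. SAP 7.1.5 sets the Group 1 efficacy baseline at or before randomization, so a Day 0 assessment done after randomization also takes the patient out. Three kinds of patient remain:

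- Group 1 patients whose Day 0 assessment was skipped or was done before randomization, and who have not reached Week 12.
- Group 2 Subgroup D patients not yet at Week 12, since no Day 0 assessment is scheduled for them.
- Patients who leave and do not attend a discontinuation visit.

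**3. How long is the Group 1 window?** Skipping Day 0 requires a disease assessment in the preceding 3 weeks. If that is the pre-randomization one (Day 80 ± 5 post-HSCT), randomization to Day 0 is at most 3 weeks. The window is 3 + 12 = 15 weeks, or 16 with the 1-week visit window.

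**4. How many Group 1 patients?** Planned accrual is 150/50 = 3 per month.

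- 15 weeks = 105/30.44 = 3.45 months; 3 × 3.45 = 10.3 patients.
- 16 weeks = 112/30.44 = 3.68 months; 3 × 3.68 = 11.0 patients.

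That is about 10-11 over both arms.

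**5. What share could skip Day 0?** Day 0 may fall on days 85-130, which is 46 possible days. Those within 21 days of the earlier assessment number 12 if it was on Day 75 (12/46 = 26%), 17 if on Day 80 (37%) and 22 if on Day 85 (48%). If Day 0 is spread evenly over those days (an assumption), 10.3 × 0.26 = 2.7 to 11.0 × 0.48 = 5.3 patients could be exposed.

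**6. Expected events lost.** The early rate of qualifying GVHD is assumed to be 5-15%.

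- Low: 2.7 × 0.05 = 0.1.
- High: 5.3 × 0.15 = 0.8.

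Allowing for leavers, this is roughly 0.1 to 1 event per analysis.

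**7. Does this arise at both Group 1 cuts?** Use exponential RFS with the plan's medians of 8 and 14.5 months, 1.5 patients per month per arm and no dropout. While accrual continues, expected events per arm at month T are 1.5 × [T − (1 − e^(−λT))/λ], with λ = ln 2/median.

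- T = 28.0: 26.2 + 18.8 = 45 events (the plan expects this near month 30).
- T = 44.9: 50.4 + 39.6 = 90 events, before the 50-month accrual ends.

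So recently randomized patients can be present at the interim and at the primary analysis.

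**8. Effect on the hazard ratio (illustration only).** A Cox simulation used 1,000 runs per scenario, 75 patients per arm, the plan's RFS medians and assumed GVHD rates. With GVHD in 10% of Arm A and 5% of Arm B, and 10% of GVHD patients having no disease assessment, about 0.8 and 0.4 events are erased. The GRFS hazard ratio is 0.610 when they are counted and 0.605 when they are censored. With 5% GVHD in both arms it moves from 0.567 to 0.565.

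**The case against.** The strongest reply is that this is a drafting slip with almost no reach. Most of that stands:

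- **Leavers are partly covered.** The note to Table 1 gives discontinuation visits the Week 24 assessments, which include a disease assessment, and Protocol 7.2 asks for such a visit where possible. Under Protocol 7.1, stopping MT-401 is not leaving the study.
- **Group 2 has its own safeguard.** Its primary analysis follows 6 months of follow-up for all treated patients, so at that point only leavers and missed visits remain in Subgroup D. Exposure is wider in any earlier cut.
- **Little depends on GRFS.** SAP 7.4.7.5 makes Group 1 GRFS descriptive, and the interim rules in SAP 7.4.7.3 use RFS. No error rate or stopping rule is touched.

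A reader might infer that any GVHD found before the first disease assessment is erased. It is not, because a later assessment before the cutoff restores the event. A reader might also infer that the lost events fall mainly in Arm A and so favour MT-401. Required Week 2 and Week 4 visits in Arm A only make that possible. But the rule is the same in both arms, SoC patients attend those visits when clinically indicated, AEs are collected from Day 0 to Week 12, and no GVHD rate is given by arm. Protocol 8.2.1 calls the product's GVHD risk very low. The simulated shifts toward MT-401 follow from the assumed RFS benefit and GVHD rates, so they are not evidence of a tilt.

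What the reply does not remove is the contradiction. The SAP repeats the rule, and SAP 7.4.7.2 widens it.

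**Conclusion.** The GRFS rules contradict each other for living patients with qualifying GVHD and no post-baseline disease assessment by the cutoff. Followed literally, the SAP deletes those events. The expected loss in Group 1 is roughly 0.1 to 1 event per analysis. That rests on planned accrual of 3 per month, an even spread of Day 0 dates and an assumed 5-15% early GVHD rate, none of which the documents establish for the actual data. No size can be given for Subgroup D. The consequence is minor: a descriptive secondary endpoint could be slightly misstated, with the direction unproven. Primary RFS is not affected. It is worth correcting because the text is wrong as written and the correction is easy.

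**What to change.** 1. State once, in Protocol 9.3.4.2 and SAP 6.4.1.3, that a qualifying GVHD event counts on its date whether or not a disease assessment was done.
2. In the Table 11 row "No on-study disease assessments and no death", add *no GVHD event* as a further condition.
3. Add *and have had no GVHD event* to the matching censoring sentences in Protocol 9.3.4.2 and SAP 6.4.1.3.
4. In SAP 7.4.7.2, add an exception for GVHD and for death where the 1-day rule is applied to GRFS.
5. State how a GVHD event ranks against the Table 11 rows for a missing baseline disease assessment and for two or more consecutive missed disease assessments. Neither has a GVHD exception. For the second, SAP 6.4.1.3 works from missed GVHD assessments while Table 11 works from missed disease assessments, so the two should be aligned.

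The cost is wording in a few rows and sentences. No new data, visits or patients are needed.

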9.3.4.3. Overall Response Rate (Group 2 Subgroup C)

Overall response rate (ORR) is defined as the proportion of treated patients who achieve a best response of CR_{MRD} -, CR, CRi, MLFS or PR using the ELN recommendations. The statistical methods for analyzing ORR are identical to those described for CR.

Duration of response is defined as the time between the date of first documented response of CR_{MRD}-, CR, CRi, MLFS or PR to the date of the first documented progression. The statistical methods for analyzing ORR are identical to those described for DOCR.

